### **I.11. Authorisation**

The document describing the study (with all its annexes, patient information, patient consent statement) is to be approved by the National Institute of Pharmacy and Nutrition (OGYÉI). The research plan is evaluated from an ethical point of view by the Scientific and Research Ethics Committee of the Medical Research Council (ETT TUKEB).

## II. Statistical analysis plan

The data shall be processed and evaluated using statistical methods adopted in the case of tests not involving intervention.

Single-variable statistical methods: frequency (distribution), relative frequency, average, standard deviation, median, lower and upper quartiles. Multivariate regression analysis is used to analyse primary and secondary endpoints, if necessary.

The statistical analysis plan contains two parts, that is, the description of methods and tools for the processing of measured breathing parameters, and the description of methods and tools for the processing of the calculated deposited doses.

### *II.1. Processing of the measured breathing data*

The analysis of the dependence of PIFdev for each selected device on patient demographic data (age, gender), anthropomorphic characteristics (height, weight), disease condition (expiratory volume at the end of the first second of forced exhalation: FEV1, forced vital capacity: FVC, Tiffeneau index: FEV1/FVC, GOLD grades) and baseline spirometric data characterizing the inhalation (peak inspiratory flow: PIF, inspiratory vital capacity: IVC, inhalation time: tin) is performed by an in-depth statistical evaluation of the interrelationships.

*Cross-correlation analysis* of the above parameters (except gender, and GOLD grades) in connection with each device is performed.

*Correlations* between different parameters are expressed by *Pearson coefficients*.

*Predictors* of PIFdev are looked for by stepwise *multiple regression analysis* using a backward elimination technique.

Mean PIFdev values of different patient subgroups upon gender, age, body mass index (BMI) and disease stages (GOLD grades) are analysed by conducting *two-sample t-tests*. Two age groups are formed. The cut-off age is 65 years. By the same token, two groups are formed upon BMI by using a cut-off value of 25 kg/m^2. Two groups are analysed also based on disease severity.

All statistical analyses are performed by the application of *OriginPro 2018* (version b9.5.0.193, OriginLab Corporation, Northampton, Massachusetts, USA) and *Minitab*® (version 18.1, Minitab, Inc., State College, Pennsylvania, USA) software packages. A value of  $p < 0.05$  is considered significant throughout the study.

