### **I.2. Characteristics of patients to be included in the study (inclusion and exclusion criteria)**

#### **Inclusion criteria**

- diagnosed obstructive lung disease (asthma or COPD)
- proper usage of inhalation tool after being educated
- availability of whole body plethysmography measurement data from the last 6 months or the possibility to perform them before the start of the study (the most important parameter is reserve volume, RV)
- subject under outpatient/inpatient therapy
- over 18 years of age
- capable of acting and cooperating

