### **I.3. Sampling and recruiting principles**

[figure not shown]
Every involved medical professional should opt for randomness in sampling. This includes the selection process but also the device order. We are involving examiners

for our test from different levels of healthcare servicing (university centre, regional institute, county hospital, panel clinic) aiming to ensure that the sampling venues (centrum related) to minimize centre specific effects.

Participation of patients is on a volunteer basis. Patient involvement in ambulant patient care occurs strictly in the time frame when the examination would take anyway place, no special visit (only for the study) will be needed. Only patients with proven records of COPD or asthma can be involved. In principle, in every centrum anyone who shows up for examination with asthma or COPD and is willing to cooperate can participate, given that it passes the inclusion criteria and no exclusion criterion applies to him/her. Children under 18 cannot be involved in the examination. There is no upper age constraint. There are no restrictions on gender or ethnicity. Minimum number of patients planned is 200.

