#### **I.5. Actions to be undertaken during the visit**

The table below summarizes the data collection during the visit. The patients can only be involved and data can be registered only if these data would have anyway been obtained through a regular visit. In addition to the patient data, the centruns' data will be registered as well in the eCRF system, as complementary data helping the evaluation of the examination.

| Patients' data collection  | visit 1 (patient involvement) |
|---|--------------------------------------|
| Time  | 0 th day                  |
| Evaluation of the inclusion and exclusion criteria  | X                                    |
| Comprehensive informing of the patient  | X                                    |
| Signing of patient information leaflet and patient consent sheet  | X                                    |
| Recording of patient demographic data   | X                                    |
| Recording of the anamnesis  | X                                    |
| Recording of diagnostic   | X                                    |
| Recording of actual status  | X                                    |
| Smoking habit   | X                                    |
| Applied drug therapy, dose  | X                                    |
| Education on the use of inhalers  | X                                    |
| Whole body plethysmography measurement, only if it was not performed in the last 6 months (recording of RV and FVC) | X                                    |
| Recording of inhalation time and breath-holding time.   | X                                    |
| Registration of eventual side effects or unexpected events.   | X                                    |

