### *II.1. Processing of the computed lung deposition data*

An analysis of the correlation of the computed lung doses with the breathing parameters characterizing the inhalation through the selected devices (Q, tb-h, IV, tin, PIFdev) is performed. The strength of the correlation is expressed in terms of *Pearson coefficients* and any correlation is considered significant when  $p < 0.05$ .

In addition, the correlation of lung deposition with baseline spirometric breathing parameters expressing the breathing status of the patient (expiratory volume at the end of the first second of forced exhalation: FEV1, forced vital capacity: FVC, Tiffeneau index: FEV1/FVC, peak inhalation flow: PIF, peak expiratory flow PEF, inspiratory vital capacity: IVC) is studied. (PIF denotes the peak inhalation flow measured by standard spirometry, while PIFdev is the peak inhalation flow measured while inhaling through the device, PIFdev < PIF).

Mean values of lung doses characteristic of different age, gender and GOLD groups are analysed conducting *two-sample t-tests*. Two age groups are formed. The cutoff age is 65 years. Two groups are analysed also upon the classification of patients based on symptoms and exacerbation history.

All statistical analyses are performed by the application of *OriginPro 2018* (version b9.5.0.193, OriginLab Corporation, Northampton, Massachusetts, USA).

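### Diagnosis (asthma or COPD) is recorded but not used in the PIFdev and lung-dose analyses, so pooled correlations with spirometry may reflect disease type

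*Combined protocol and SAP*

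**What the plan says.** Protocol I.2 accepts either disease, and I.3 adds that "anyone who shows up for examination with asthma or COPD and is willing to cooperate can participate", subject to the eligibility criteria. No quota or planned share per disease is given. The visit table in I.5 includes "Recording of diagnostic".

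The SAP has two sections numbered II.1. The first, on measured breathing data, plans "The analysis of the dependence of PIFdev for each selected device on patient demographic data (age, gender), anthropomorphic characteristics (height, weight), disease condition". Its own parenthesis defines disease condition as FEV1, FVC, FEV1/FVC and GOLD grades. PIF, IVC and inhalation time follow as further variables. A cross-correlation "of the above parameters (except gender, and GOLD grades) in connection with each device is performed". Predictors of PIFdev are then sought by backward elimination, and t-tests compare groups by gender, age, BMI and GOLD grade.

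The second, on computed lung deposition, correlates lung dose with five inhalation parameters measured through the device. It also studies "the correlation of lung deposition with baseline spirometric breathing parameters expressing the breathing status of the patient", meaning FEV1, FVC, FEV1/FVC, PIF, PEF and IVC. Its t-tests use age, gender and GOLD groups, and it adds: "Two groups are analysed also upon the classification of patients based on symptoms and exacerbation history".

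The SAP introduction says only: "Multivariate regression analysis is used to analyse primary and secondary endpoints, if necessary". It names no covariates.

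**The concern.** Asthma and COPD patients may differ both in baseline spirometry and in PIFdev or lung dose. If they do, a correlation computed across both groups contains a between-disease part. It can then be non-zero when nothing is associated within either disease, or near zero when something is.

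This bears on the first secondary goal, which relates lung deposition efficiency to the patient's current health status. The SAP serves that goal partly through lung dose against FEV1, FVC and FEV1/FVC. A reader who takes such a coefficient as an effect of severity needs to know whether it holds within asthma and within COPD, and the SAP commits to no step that would show this. Section I.9 intends significant differences in deposition to feed research on personal inhaler choice, which makes that reading likely.

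**Working it through.** The plan gives no figure on this point, so there is none to reproduce. Steps 1 and 2 compare the text; steps 3 to 6 illustrate size under assumptions.

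**1. Recorded against used.** Diagnosis is recorded (I.5).
- PIFdev variables: age, gender, height, weight, FEV1, FVC, FEV1/FVC, GOLD grades, PIF, IVC, inhalation time; BMI for grouping.
- Lung-dose variables: Q, breath-hold time, inhaled volume, inhalation time, PIFdev, FEV1, FVC, FEV1/FVC, PIF, PEF, IVC; age, gender, GOLD and symptom/exacerbation groups.

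Diagnosis is in neither list. The first II.1 analyses by device, and I.8 sets its group minimum per medicine and device. Nothing is set per disease.

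**2. Who enters the regression.** GOLD grades are left out of the cross-correlation but not out of the regression. The bibliography identifies GOLD as the COPD initiative. If asthma patients have no GOLD grade, a complete-case model with GOLD as a candidate drops them. If they are given a value, or GOLD is not used, the model is pooled. The SAP does not say which.

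**3. Pooled correlation when the within-disease correlation is zero.** Let p be the share with one disease, q = 1 − p, ρ the within-disease correlation, and d1 and d2 the between-disease gaps in spirometry and outcome, in within-disease SDs:

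r = (ρ + pq·d1·d2) / √[(1 + pq·d1²)(1 + pq·d2²)]

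Assumed: p = 0.5 (pq = 0.25), ρ = 0 and the three gap pairs below. From the documents: n = 30 (I.8 minimum per medicine and device), n = 200 (I.3 minimum, relevant only if every patient uses that device) and the 0.05 level, taken as two-sided. Example for gaps 1.0 and 0.5: 0.125 / √(1.25 × 1.0625) = 0.108. The chance of p<0.05 is 1 − Φ(1.96 − m) + Φ(−1.96 − m), with m = atanh(r)·√(n − 3).

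| d1, d2 | pooled r | n = 30 | n = 200 |
|---|---|---|---|
| 0.5, 0.3 | 0.036 | 5.4% | 8.0% |
| 1.0, 0.5 | 0.108 | 8.7% | 33.3% |
| 1.5, 0.8 | 0.223 | 21.8% | 88.9% |

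At a 30:70 mix the figures are 5.3%, 7.7% and 17.7% at n = 30, and 7.1%, 25.8% and 79.2% at n = 200.

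**4. Pooled correlation when the within-disease correlation is 0.30.** With p = 0.5, pooled r is 0.25 to 0.32 for the small gaps, 0.15 to 0.37 for the middle and 0.00 to 0.45 for the large. The lower end applies when the two gaps run in opposite directions. For the large gaps the numerator is then 0.30 − 0.25 × 1.5 × 0.8 = 0. At n = 100 (illustrative) the chance of p<0.05 is 86% for r = 0.30, 33% for 0.15 and 5% for 0.00.

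**5. Backward elimination, if the model is pooled.** Simulated with a 50:50 mix, ρ = 0, FEV1/FVC plus four other candidates, and removal at p>0.05 (the SAP states no threshold). If the other candidates are unrelated to disease and diagnosis is absent, FEV1/FVC is retained at n = 200 in 33.0% of samples (middle gaps) and 89.7% (large). If the other candidates also differ by 1.0 to 1.5 SD, repeated simulations gave about 12–21% and 36–64%. At n = 30 with large gaps, retention falls from about 24% to 15–17%. With unrelated candidates and diagnosis kept in, it is 4.5–5.7% in all these settings. At n = 30 with large gaps, a diagnosis term that may itself be eliminated leaves 12.4%.

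**6. Precision by diagnosis.** For r = 0.30 with 15 patients per disease: atanh(0.30) = 0.310 and 1.96/√12 = 0.566, so the 95% CI is −0.25 to 0.70. With 9 patients it is −0.45 to 0.80, and with 100 it is 0.11 to 0.47.

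**The case against.** A reader might infer that the SAP prescribes one pooled regression. It does not: it is silent, and with GOLD grades among the candidates the model may cover COPD patients only. For the same reason, simply adding diagnosis would fail. In a COPD-only model the term is constant, and if asthma is coded as an extra GOLD category it is collinear with the GOLD indicators. Both objections stand and shape the fix.

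A reader might also take the 33% and 90% retention rates at n = 200 as the regression's false-positive rate. They depend on the other candidates being unrelated to disease, and they drop considerably otherwise. Some inflation remains.

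It can be said that the optional regression could include diagnosis. It could, so the plan does not rule out adjustment, but it commits to none. Grouping by medicine might partly separate the diseases, but no section says so, and the first II.1 works by device.

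Finally, the secondary goal asks for a correlation with health status, not a within-disease effect; every gap is assumed; and at 30 patients the inflation is negligible to moderate. All true. These points limit the concern to interpretation of secondary results. They do not remove it, because diagnosis is already recorded and the correlations, as written, mix the diseases.

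**Conclusion.** The concern holds for the Pearson correlations of PIFdev and lung dose with baseline spirometry: as written they cover both diseases, and they can reflect asthma-versus-COPD differences or mask an association within a disease. For the PIFdev regression it holds only if that model is pooled, which the SAP leaves open.

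The size cannot be fixed, since the documents give neither the disease mix nor any between-disease gap. Under the assumptions in step 3 the effect runs from negligible (small gaps) to large (wide gaps with many patients on one device). The upper end is not a prediction for this study.

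Two stronger conclusions are not supported. The pooled correlations are not invalid; they properly describe the mixed cohort. The primary aim, individual deposition modelling, is not affected.

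**What to change.** Change the SAP wording as follows.

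1. Fit the PIFdev regression in all patients without GOLD grades as a candidate, with diagnosis as a factor kept in throughout backward elimination. Use GOLD grades only in a separate COPD-only model. Include diagnosis in any lung-dose regression run under the SAP introduction.
2. Beside each pooled value, report by diagnosis, with 95% CI and labelled descriptive, the correlations of PIFdev and lung dose with the baseline spirometry listed in the two II.1 sections. This includes PIF and IVC, and PEF for lung dose.
3. As clarification, state how patients with both diagnoses are classed (I.2 does not exclude them), and which patients enter the GOLD and symptom/exacerbation comparisons.

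No new data are needed. The costs are:
- one more regression parameter and one additional COPD-only model;
- a classification rule for patients with both diagnoses;
- by-diagnosis values too imprecise at about 30 patients per device to settle whether an association holds within a disease (step 6);
- more coefficients. Five spirometric measures for PIFdev and six for lung dose, in two diagnoses, add (5 + 6) × 2 = 22 per device, or 24 if inhalation time is counted as spirometry. The SAP already implies about 56: ten variables give 45 pairs in the first II.1, and the second adds 5 + 6 = 11. No multiplicity control is stated, hence the descriptive label.

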### *II.1. Processing of the computed lung deposition data*

An analysis of the correlation of the computed lung doses with the breathing parameters characterizing the inhalation through the selected devices (Q, tb-h, IV, tin, PIFdev) is performed. The strength of the correlation is expressed in terms of *Pearson coefficients* and any correlation is considered significant when  $p < 0.05$ .

In addition, the correlation of lung deposition with baseline spirometric breathing parameters expressing the breathing status of the patient (expiratory volume at the end of the first second of forced exhalation: FEV1, forced vital capacity: FVC, Tiffeneau index: FEV1/FVC, peak inhalation flow: PIF, peak expiratory flow PEF, inspiratory vital capacity: IVC) is studied. (PIF denotes the peak inhalation flow measured by standard spirometry, while PIFdev is the peak inhalation flow measured while inhaling through the device, PIFdev < PIF).

Mean values of lung doses characteristic of different age, gender and GOLD groups are analysed conducting *two-sample t-tests*. Two age groups are formed. The cutoff age is 65 years. Two groups are analysed also upon the classification of patients based on symptoms and exacerbation history.

All statistical analyses are performed by the application of *OriginPro 2018* (version b9.5.0.193, OriginLab Corporation, Northampton, Massachusetts, USA).

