#### **Secondary goals**

- Examination of the correlation between the lung deposition efficiency (the dose depositing in the lungs divided by the dose metered in the inhalation device) and the patients current health status.
- Evaluation of patients' inhalation device usage and suggestions for optimal usage according to the acquired breathing data and calculated lung deposition values.

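### No analysis specified for secondary goal 2 can locate an optimum or a plateau: the lung-dose section names only Pearson coefficients, and the optional regression has no stated form

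*Combined protocol and SAP*

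**What the plan says.** - **The goal.** Protocol I.1, Secondary goals, lists: "Evaluation of patients' inhalation device usage and suggestions for optimal usage according to the acquired breathing data and calculated lung deposition values".
- **The analysis of lung dose against inhalation.** The SAP section on processing the computed lung deposition data says that an analysis of the correlation of "computed lung doses with the breathing parameters characterizing the inhalation through the selected devices (Q, tb-h, IV, tin, PIFdev) is performed". It continues: "The strength of the correlation is expressed in terms of *Pearson coefficients* and any correlation is considered significant", with the threshold at p < 0.05. The section names no curve, quadratic or spline term, rank correlation, plot or linearity check. Its t-tests compare lung dose between age, gender, GOLD and symptom/exacerbation groups, not between levels of flow, volume or breath-hold.
- **The regressions.** The SAP introduction says: "Multivariate regression analysis is used to analyse primary and secondary endpoints, if necessary". It gives no outcome, covariates or functional form. The one regression set out in detail is in the section on measured breathing data and has a different outcome: "Predictors* of PIFdev are looked for by stepwise *multiple regression analysis* using a backward elimination technique".
- **Sizes.** Protocol I.3: "Minimum number of patients planned is 200". Protocol I.8 permits interim analysis and publication from 30 patients per medicine and device. It also provides for deposition to be modelled for individual patients.

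**The concern.** An optimal way of using a device is a value of flow, volume or time. It may lie inside the range, with dose lost on both sides, or be a point after which more adds nothing. A Pearson coefficient answers a different question: whether dose tends to rise or fall along a straight line. Even a highly significant r does not answer goal 2.

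Two things could go wrong if the relation bends within the patients' range. With an optimum near the middle, r can be close to zero although the relation is strong. With an optimum off-centre, or a plateau, r can be clearly positive while some patients are already past the useful point. With no plot or linearity check planned, the study would not find out which case applies.

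**Working it through.** The documents give no effect size, power or dose-flow curve, so there is no figure to reproduce. What can be checked is how Pearson behaves under curved relations. Every curve shape, distribution and R² below is an assumption. So is reading Q as flow, IV as inhaled volume and tb-h as breath-hold time. From the documents come the 0.05 level (two-sided assumed), n = 30 per product and the total of 200.

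**1. Critical value.** |r| = t/√(n − 2 + t²), where t is the 97.5% point on n − 2 df.
- n = 30: 2.048/√(28 + 4.196) = 0.361.
- n = 200: 1.972/√(198 + 3.889) = 0.139.

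**2. Noise-free curves, parameter uniform on 0 to 1.** For dose = −(x − m)², the covariance with x is (2m − 1)/12 and the dose variance is v = 4/45 − m/3 + m²/3. Hence r = [(2m − 1)/12]/√(v/12).
- m = 0.5: r = 0.00.
- m = 0.7: v = 0.0889 − 0.2333 + 0.1633 = 0.0189, so r = 0.0333/0.0397 = 0.84.
- m = 0.6 and m = 0.8: r = 0.61 and 0.92.
- m = 1, so that all patients are on one side: r = 0.97, and the sign is right.

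For a plateau, dose = min(x, k): r = 0.63, 0.75, 0.89 and 0.97 for k = 0.2, 0.3, 0.5 and 0.7. None of these values shows where the gain stops.

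**3. Power with noise.** Assume flow z ~ N(0,1), an optimum at d SD above the mean, and a curve explaining 30% of dose variance. The true correlation is r = √0.3 × 2d/√(2 + 4d²). Ranges are across repeated simulations, n = 30.

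| Optimum at | True r | Pearson significant | 2-df test (z and z²) significant |
|---|---|---|---|
| mean | 0 | 15–18% | 73–74% |
| 0.5 SD | 0.32 | 42–45% | 74–75% |
| 1 SD | 0.45 | 69–70% | 76–77% |
| 1.5 SD | 0.50 | 80% | 79% |

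More patients do not rescue the first row: at n = 200 Pearson is significant in about 18% of runs, with the sign split evenly. In the second row at n = 200 it is significant and positive in 98% of runs, although P(Z > 0.5) = 31% of patients lie beyond the optimum.

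If flow is uniform instead, a mid-range optimum gives Pearson significance in only 6.5–10% of runs at n = 30 or 200, for R² of 0.3 to 0.7. An optimum at 0.7 of the range gives a significant positive r in 75% of runs (n = 30, R² = 0.3).

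**4. What a curved fit can deliver at n = 30.** Under the normal-flow model, the curvature term alone is significant in 63% of runs (optimum at 0.5 SD) and 41% (1 SD). Among runs with a downward curve, the central 95% of fitted peaks spans about −0.04 to 2.7 SD and 0.2 to 7 SD respectively. For uniform plateaus from 0.3 and 0.5 of the range (R² = 0.3), a quadratic term is significant in 49% and 29% of runs. If the truth is a straight line with r = 0.4, the 2-df test has 49–50% power against 61–62% for Pearson.

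**The case against.** The strongest defence has four parts.

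- **The link is inferred.** The protocol does not say that the usage suggestions come from the correlation table. A reader might infer that advice will rest on the sign or p-value of r. Nothing in the documents says so, and Pearson is an ordinary descriptive measure of correlation. This stands.
- **Other routes exist.** Regression is allowed if needed, and per-patient deposition modelling is foreseen. It is therefore too strong to say that Pearson is the only analysis open to the study. But the regression clause has no form, and linear terms alone would share the limit. No section describes running the model over alternative inhalation manoeuvres or names the analysis behind goal 2. These routes soften the point without closing the gap.
- **The harm rests on assumed shapes.** This stands. The large power gap needs the optimum near the patients' mean. At 1 SD it is small and at 1.5 SD it has gone. For a plateau, r of 0.63 to 0.97 is a strong correlation, not a missed relation.
- **A curved fit has limits too.** At 30 patients the location of a peak is poorly determined. A one-variable curve across different patients does not by itself show what happens when one patient changes technique, especially if flow, volume and time are tied together. This also stands, and it shapes the fix.

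**Conclusion.** The point holds as a gap in specification. Goal 2 needs a location, and no analysis specified in the SAP can give one: the lung-dose section names a linear coefficient, and the regression clause has no form. That conclusion does not depend on the true curve.

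A reader might go further and infer that the planned analysis will miss or reverse a strong relation. The documents do not support that, because they do not show that an optimum or plateau lies within the observed range. If one lies near the centre, the loss is large (about 16% against 74% at n = 30, under a quadratic explaining 30% of variance). If the patients lie mostly on one side of it, Pearson loses little and its sign is right.

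**What to change.** In the SAP section on computed lung deposition data:

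1. Keep the Pearson table.
2. For each product, plot lung dose against each of the five parameters. Add a quadratic or 3-knot spline fit with its 95% confidence band. For breath-hold use a spline on the original time scale. A log term bends but never levels off, so it cannot find a plateau.
3. Name the analysis that serves goal 2, and state that usage suggestions will not rest on the sign or p-value of r.
4. Report any peak or levelling-off point with its interval and as a between-patient description.
5. State that a non-significant curvature test at about 30 patients per product will not be read as proof of a straight line.

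The cost is SAP wording, a few more fits and one extra parameter per relation. Under a straight-line truth the 2-df test is weaker than Pearson, which is why the Pearson table stays. In small product groups the interval for a peak will often be wide, and the report should show it.

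### For lung dose, the SAP pre-specifies age only as a two-group split at 65 years, although it keeps age continuous for PIFdev

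*Combined protocol and SAP*

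**What the plan says.** Two SAP subsections carry the number II.1, so I refer to them by title.

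**Processing of the computed lung deposition data.** Pearson correlations with lung dose are planned for two lists of variables. The first holds the through-device parameters (Q, tb-h, IV, tin, PIFdev). The second covers "the correlation of lung deposition with baseline spirometric breathing parameters expressing the breathing status of the patient", namely FEV1, FVC, FEV1/FVC, PIF, PEF and IVC. Age is in neither list. It appears in the next paragraph: "Mean values of lung doses characteristic of different age, gender and GOLD groups are analysed conducting" two-sample t-tests, followed by "Two age groups are formed. The cutoff age is 65 years". A further grouping is then given: "Two groups are analysed also upon the classification of patients based on symptoms and exacerbation history".

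**Processing of the measured breathing data.** Age is among the factors whose relation to PIFdev is studied. A cross-correlation analysis "of the above parameters (except gender, and GOLD grades) in connection with each device is performed", so age is included as a continuous variable. Predictors of PIFdev are also sought by backward-elimination regression. The split at 65 is made here as well, together with a BMI split. For severity the text says only: "Two groups are analysed also based on disease severity".

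**Opening of the SAP.** "Multivariate regression analysis is used to analyse primary and secondary endpoints, if necessary".

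**The concern.** Lung deposition is the subject of the primary aim (Protocol I.1). For this quantity the plan uses age less fully than for PIFdev, an intermediate measurement, and gives no reason. A split at 65 treats all patients on one side of the cut as alike, and patients aged 64 and 66 as different in kind. If lung dose changes gradually with age, a t-test on the two groups has less power than an analysis of age itself, from the same patients. A real gradient could be missed.

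There is also a smaller gap. Neither subsection says which categories are merged to form the two severity groups (PIFdev) or the two symptom/exacerbation groups (lung dose). The merging is therefore open until the data are seen.

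**Working it through.** The documents state no power, effect size or information figure, so there is nothing of theirs to reproduce.

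**Inputs from the documents**
- Cut at 65 years (SAP, lung deposition subsection).
- Minimum of 200 patients (Protocol I.3).
- At least 30 patients per medicine and device for interim analysis and publication (Protocol I.8).
- Adults with asthma or COPD, with no upper age limit (Protocol I.2 and I.3).
- A p-value below 0.05 "is considered significant throughout the study"; sidedness is not stated.

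**Assumptions of mine**
- Age is normally distributed and its effect on lung dose is linear.
- Tests are two-sided.
- The share of patients on each side of 65 is unknown, so a range is shown. The number of patients per device is also not stated, so both 200 and 30 are shown.

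**Step 1: information kept by the split.** With share p on one side of the cut and c the corresponding normal quantile, the fraction kept is φ(c)² / [p(1−p)].
- 50/50: 0.3989² / 0.25 = 0.637, a loss of 36%.
- 70/30: 0.3477² / 0.21 = 0.576, a loss of 42%.
- 80/20: 0.2800² / 0.16 = 0.490, a loss of 51%.

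**Step 2: equivalent number of patients.**
- 200 × 0.637 = 127; 200 × 0.576 = 115; 200 × 0.490 = 98.
- 30 × 0.637 = 19; 30 × 0.576 = 17; 30 × 0.490 = 15.

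**Step 3: power.** By the Fisher z approximation, power = Φ(atanh(r)·√(n−3) − 1.96). After the split, r is multiplied by the square root of the fraction kept. The correlations are illustrative.

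| n | true r | continuous age | 50/50 | 70/30 | 80/20 |
|---|---|---|---|---|---|
| 200 | 0.20 | 81% | 62% | 57% | 51% |
| 200 | 0.30 | 99% | 93% | 90% | 85% |
| 30 | 0.50 | 81% | 59% | 55% | 48% |

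Worked example, n = 200, r = 0.20: atanh(0.20) = 0.2027; 0.2027 × √197 = 2.85; Φ(0.89) = 81%. At 50/50, r becomes 0.20 × √0.637 = 0.160; 0.161 × √197 = 2.26; Φ(0.30) = 62%.

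**Step 4: other age shapes, cut at 65, linear effect.** The loss is 1 minus the squared correlation between age and the two-group indicator.
- Uniform 40–90: 25%. For a uniform age the fraction kept is 3p(1−p), here 3 × 0.25 = 0.75.
- Uniform 18–90: 32%.
- Normal, truncated to 18–95: mean 65, SD 9, 36%; mean 60, SD 12, 40%; mean 55, SD 15, 45%; mean 50, SD 15, 54%.
- Normal, mean 50, SD 15, not truncated: 56%. The share above 65 is 0.159, and 0.242² / (0.159 × 0.841) = 0.44 is kept.
- Half normal with mean 45, SD 12 and half normal with mean 68, SD 8: 42%.

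**The case against.** **What can be said for the plan.** Neither the primary aim nor the secondary goals mention age. The goal on current health status is served in the lung-dose subsection by continuous FEV1, FVC and FEV1/FVC, so the age comparison is peripheral. This stands: it limits the weight of the point but does not remove it, because the plan chose to test age and the better test is nearly free.

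**The general regression provision** could include continuous age. But it is conditional, and it names no covariates, coding or trigger. It permits such an analysis without pre-specifying one.

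**The percentage rests on assumptions.** This stands in full. The documents give no mean, SD or share above 65. The effect is also assumed linear; if lung dose really changed in a step at 65, the split would lose nothing.

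**Stronger readings that the documents do not support**
- A reader might apply the 36–51% loss to the GOLD groups. The formula is for a normally distributed predictor, and GOLD is categorical.
- A reader might infer that ordered GOLD grades are cut in two for lung dose, that trying every cut would inflate false positives by a known amount, and that an ordered score would cure it. For lung dose the groups come from symptoms and exacerbation history, and the text gives no single ordered scale. An undefined grouping permits a choice after the data are seen; it does not show that one will be made.
- A reader might infer that disease severity is reduced to two groups. The spirometric measures stay continuous against lung dose.
- A reader might object to the BMI split. BMI is not in the lung-dose subsection, and for PIFdev height and weight enter as continuous variables.

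**Conclusion.** The point holds for age in the lung-dose analysis. Its only pre-specified use there is a t-test split at 65, while the same SAP keeps age continuous for PIFdev. Under a normal age distribution and a linear effect, the cost is about 36% of the information on age at a 50/50 split and 51% at 80/20, so 200 patients act like about 127 to 98. Other plausible shapes give about 25% to 56%. The exact figure cannot be known from the documents, but the loss is material under every shape tried, given a linear effect.

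This is a loss of precision, not a bias or an inflated error rate: the age cut is fixed in advance. The undefined severity and symptom/exacerbation groups are a secondary point about pre-specification, and no percentage is attached to them.

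**What to change.** In the lung deposition subsection, add that lung dose is analysed per device against age as a continuous variable, by Pearson correlation or by regression with the slope given per 10 years and a confidence interval. Make this the inferential analysis for age, and keep the 65-year split for descriptive tables only.

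In both subsections, state before analysis which categories form each of the two groups (severity for PIFdev, symptoms and exacerbation history for lung dose), or compare all categories.

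The cost is SAP wording. Demographic data are already on the visit schedule (Protocol I.5), and the Pearson method and software are already named in the same subsection. No extra patients, measurements or visits are needed.
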